### **Subgroup analyses**

The following subgroups will be explored:

- Smoking status: Smoke / Never Smoke
- Gender: Male / Female
- Age: Age  $\leq 65$  / Age  $> 65$
- Stratification factor: With / Without background therapy
- % predicted FVC categories at baseline (using terciles ( $\leq 60$ ,  $> 60$  and  $\leq 75$ ,  $> 75$ ))
- ANA at baseline: Positive / Negative where a Positive ANA titer is defined as titer  $\geq 1:40$

For each pool of active arm vs placebo (A and B), the subgroup-by-treatment interaction will be tested using a Cox model containing in addition the subgroup variable and the subgroup-by-treatment interaction to be tested. When the stratification factor is the subgroup to be tested, the model should not be stratified by this stratification factor.

Descriptive statistics including number (%) of patients, number of events, event rates, HR, 95% CI by subgroup will be reported by treatment arm.

In addition, a forest plot will resume the HR and corresponding 95% CIs of each active arm versus placebo by subgroup.

#### 2.4.4.2.2 *All-cause mortality endpoint*

The all-cause mortality will be analyzed on the mITT population. Deaths from baseline to week 52 (performed before Day 375) will be used regardless of whether the patient has previously discontinued treatment.

The cumulative incidence of all-cause mortality will be presented graphically by treatment arm and background therapy status, using Kaplan-Meier method. The Kaplan Meier survival estimates (number of patients at risk, number of patients censored, number of death events and probability of surviving without event (95% CI)) will be summarized by time points and overall (number of patients censored, number of events, median time to event).

The censoring reasons will be described by treatment arm and background therapy status.

The event rates for each of the 3 treatment arms, the hazard ratio and its 90% and 95% CIs compared to placebo for each active arm versus Placebo will be estimated from a Cox model containing the treatment and the stratification factor variables. The underlying assumption of proportional hazards for Cox model will be checked by visual inspection.

No hypothesis testing will be performed as per protocol.

The same time-to-event analysis with IPF-related deaths only will be explored on the mITT population.

#### 2.4.4.2.3 *Exploratory endpoints*

##### 2.4.4.2.3.1 *Acute IPF exacerbations endpoint*

The number of acute IPF exacerbations and the number of patients having one, two or more than two acute IPF exacerbations will be described in the mITT population by treatment arm and background therapy status.

The annual rate in patient-year by treatment arm, the rate ratio and its 90% CI for each active arm versus placebo will be determined using a negative binomial model adjusted on the stratification factor variable and containing the stratification factor-by-treatment interaction. The SAR156597 qw arm will be tested versus Placebo at a type I error level of 10% first and if significant, will the SAR156597 q2w arm be tested versus Placebo at a two-sided type I error level of 10%.

In addition, a description of the following items will be performed by treatment arm and by background therapy status for events occurring between randomization and Day 375:

- the number (%) of patients with any IPF event (complementary form filled whatever the final diagnosis question answer),
- the number (%) of patients with acute IPF exacerbation (final diagnosis question is equal to “yes”),

- the other diagnoses (final diagnosis question is equal to “no”, with associated PT term and verbatim),
- the clinical evaluation,
- the radiology assessment
- and any corrective treatment/therapy used.

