8.4 METHOD OF ASSIGNING PATIENTS TO TREATMENT GROUP

Patient will be randomized following a 1:1:1 ratio to one of the three treatment arms via a centralized randomization system using IVRS/IWRS.

A randomized treatment kit number list will be generated centrally by Sanofi. The investigational product (SAR156597 or placebo) will be packaged in accordance with this list.

At V1 (screening) the study staff will contact the IVRS/IWRS to obtain a patient number for each patient who gives informed consent.

The result from the central reviewer on diagnosis of IPF have to be obtained to validate the inclusion of patient before randomization as per inclusion criteria (See section [Section 7.1](#))

The population will be stratified according to background therapy at the moment of randomization:

- Patient with background therapy with either pirfenidone or nintedanib
- versus patient without background therapy
- It is planned to include a maximum of 66% of patients with background therapy.

Randomization will be performed at Visit 2 (Day 1) by a centralized randomization procedure using IVRS/IWRS.

Patients who comply with all inclusion/exclusion criteria will be assigned before the IMP administration on Visit 2 (Day 1):

- A treatment number in a preplanned order following the randomization list, and
- A patient number according to the chronological order of inclusion.

A patient cannot be randomized more than once in the clinical trial.

Patients who meet exclusion criteria may be re-screened once during the open screening period of study; a different patient identification will be issued. Re-screening is not permitted if the patient fails to meet inclusion criteria. There is no requirement for a waiting period between the screen-failure date and the re-screening date. The IVRs/IWRS report will flag re-screened patients. Patients that are re-screened must sign a new consent form and all Visit 1 procedures must be repeated.

The treatment kits are sufficient for 2 weeks of treatment. As the treatment duration is 52 weeks, a patient will be allocated by the IVRS to several treatment kit numbers corresponding to the same treatment arm assigned from randomization.

The details of the centralized randomization procedure and IVRS are provided in a separate manual.

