### **1.3 DETERMINATION OF SAMPLE SIZE**

Approximately 300 patients will be randomized in this study, 100 per treatment arm. Based on the enrollment in prior studies of this population approximately half of the patients are expected to be older than 65.

The sample size calculations are based on the primary efficacy variable of % predicted FVC change from baseline to week 52, with the following assumptions:

- A common standard deviation of 12% is assumed based on the data from previous trials (26)
- A 5% mean difference between each dose and placebo in change from baseline in % predicted FVC
- A 2-sided 5% significance level with 80% power

Ninety two (92) patients per treatment arm will yield 80% power to detect a 5 percentage point difference between the treatment groups and placebo. Additional patients will be randomized in each regimen to allow for dropouts; therefore, approximately 100 patients will be randomized into each treatment arm, for a total sample size of approximately 300 patients for the study.

[figure not shown]
As a rank-based method will be used for analysis the actual power may differ from these calculations, however, calculations based on the ASCEND study (28), which used the same analysis method and endpoint confirm that the planned analysis should have at least 80% power. No adjustment is made for multiplicity since a hierarchical testing procedure is proposed.

Calculations were made using nQuery Advisor 7.0.

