#### 2.1.3.2.4 *Exploratory efficacy endpoints*

The other secondary efficacy endpoints are considered exploratory and include:

- Rate of acute IPF exacerbations at 52 weeks in the mITT population
- Rate of respiratory hospitalizations and rate of non-elective hospitalizations at 52 weeks in the mITT population
- Change from baseline in 6-MWT distance at 52 weeks in the mITT population
- Change from baseline in HRCT lung interstitial score at 52 weeks in the mITT population
- Change from baseline in the total score of the SGRQ at 52 weeks in the mITT population
- Change from baseline in the total score of the EQ-5D-5L at 52 weeks in the mITT population

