#### 2.1.3.2.5 *Acute IPF exacerbations endpoint*

All acute IPF exacerbations events are recorded during the study on the AE e-CRF page. To help the investigator in diagnosing an acute IPF exacerbation, an “IPF Exacerbation Complementary” e-CRF form has to be completed.

For efficacy analysis, only acute IPF exacerbations with a confirmed diagnosis on the “IPF Exacerbation Complementary” e-CRF form and occurring from randomization to Day 375 will be considered.

In addition, the following information is recorded on this complementary form:

- Diagnosis of AE,
- Clinical evaluations
  - unexplained worsening or development of dyspnea within 30 days,
    - if no what is the symptom or finding of the patient related to this AE,
  - worsening of hypoxemia from a known baseline arterial blood gas,
  - pulmonary infection ruled out by endotracheal aspiration or broncho-alveolar lavage (BAL),
    - if no, was pulmonary infection ruled out by routine clinical practice and/or microbiological studies
  - have alternative causes (including left heart failure, P.E., acute lung injury, tec.) been excluded
- Radiology assessment
  - HRCT performed
    - If yes, did it show new ground-glass abnormality and/or consolidation consistent with a UIP pattern

- Final diagnosis
  - Based on response provided, do you believe that the patient experienced an acute IPF exacerbation
- Management
  - Was corrective treatment/therapy used

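### The exacerbation model includes a stratum-by-treatment interaction with no stratum weights, test type or sparse-cell rule, so an empty arm-by-stratum cell can leave an exploratory rate ratio and its gated test not estimable

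*SAP*

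**What the plan says.** For acute exacerbations, SAP 2.4.4.2.3.1 derives the annual rate per arm and "the rate ratio and its 90% CI for each active arm versus placebo" from a "negative binomial model adjusted on the stratification factor variable and containing the stratification factor-by-treatment interaction". The tests come from the same model: "The SAR156597 qw arm will be tested versus Placebo at a type I error level of 10% first", with q2w tested only if qw is significant. Appendix B repeats the model with the interaction.

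The endpoint is exploratory (SAP 2.1.3.2.4: "The other secondary efficacy endpoints are considered exploratory and include"). Only confirmed exacerbations "occurring from randomization to Day 375 will be considered" (SAP 2.1.3.2.5).

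On cell sizes, SAP 1.3 says "Approximately 300 patients will be randomized in this study, 100 per treatment arm". Protocol 8.4 says "It is planned to include a maximum of 66% of patients with background therapy".

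The SAP does not say how the rate ratio is averaged over strata, whether the test is Wald, score or likelihood ratio, or what happens if a cell has no events or the model does not converge. Section 2.5.7, on statistical technical issues, reads as not applicable. Neither document gives an expected exacerbation rate.

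Two other parts of the SAP bear on the point. The 52-week Cox models for disease progression (2.4.4.2.1) and all-cause mortality (2.4.4.2.2) contain treatment and stratum only. Section 2.4.4.2.3.1 already plans exacerbation counts by arm and by background therapy status.

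**The concern.** Three arms by two strata with the interaction is a saturated model, so each of the six cells has its own rate. If a cell has no exacerbations, its fitted rate is zero and its log rate is minus infinity. A treatment effect formed by averaging stratum-specific log rate ratios then has no finite estimate. What the software prints depends on when the iterations stop.

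Which results are lost depends on the cell:

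- **Empty qw cell:** the qw contrast is lost. The Wald p-value goes to 1, so the hierarchy also blocks the q2w test.
- **Empty placebo cell:** both contrasts are lost.
- **Empty q2w cell:** the q2w contrast is lost and the qw contrast is intact.

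An arm with fewer events than placebo could thus be reported as showing nothing because one of its cells was empty. Any rescue chosen after unblinding would be post hoc. Even with events in every cell, an interaction model yields no single rate ratio per arm until stratum weights are stated.

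**Working it through.** **The plan's own figure.** The only sample-size calculation is for the primary endpoint: a 5-point difference, SD 12, two-sided 5%, 80% power. The normal approximation gives 91 per arm. The t-based calculation gives 91.4, so 92, with power 0.803 at 92. The stated 92 is reproduced, but it says nothing about exacerbations.

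**Inputs for the cell check.**
- Patients per arm: 100 (SAP 1.3).
- Stratum split: 66/34, the Protocol 8.4 cap.
- Follow-up: T = 375/365.25 = 1.027 years, the full window in SAP 2.1.3.2.5. No dropout is assumed.
- Rate r: not in the documents, so varied and assumed equal in all cells.

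**Formulas.** For Poisson counts, the probability that a cell of n patients is empty is p(n) = exp(−n·r·T). Then:
- qw versus placebo (four cells): 1 − [(1 − p34)(1 − p66)]²
- any of six cells: 1 − [(1 − p34)(1 − p66)]³

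At r = 0.05, p34 = exp(−1.75) = 0.175 and p66 = exp(−3.39) = 0.034. The product (1 − 0.175)(1 − 0.034) is 0.797. This gives 1 − 0.797² = 0.36 and 1 − 0.797³ = 0.49.

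| Rate per patient-year | Expected events, n=34 / n=66 | p34 | p66 | Any of 4 (qw vs placebo) | Any of 6 |
|---|---|---|---|---|---|
| 0.03 | 1.05 / 2.03 | 0.351 | 0.131 | 68% | 82% |
| 0.05 | 1.75 / 3.39 | 0.175 | 0.034 | 36% | 49% |
| 0.08 | 2.79 / 5.42 | 0.061 | 0.004 | 13% | 18% |
| 0.10 | 3.49 / 6.78 | 0.031 | 0.001 | 6% | 9% |
| 0.15 | 5.24 / 10.16 | 0.005 | 0.000 | 1% | 2% |

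**Sensitivity.**
- Overdispersion, with p(n) = (1 + k·r·T)^(−n/k) and k from 0 to 3: four-cell risk 36–41% at 0.05 and 6–10% at 0.10; six-cell risk 2–4% at 0.15.
- Both active arms halve the placebo rate (k = 0 to 1): four-cell risk 62–63% at placebo 0.05 and 23–24% at placebo 0.10.
- Mean follow-up of 0.9 years (an assumed allowance for dropout, Poisson): six-cell risk 88%, 59%, 26% and 14% at 0.03, 0.05, 0.08 and 0.10.
- 50/50 split (k = 0 to 3): six-cell risk 38–44% at 0.05 and 4–7% at 0.10.

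**What the fit does.** This illustration uses invented counts, dispersion fixed at 1, an empty qw cell in the stratum without background therapy, and strata averaged equally. The qw log rate ratio was −5.6, −10.6 and −15.6 after 10, 20 and 30 iterations. Its standard error was 43, 6,438 and 958,303. The 90% CI became 0 to infinity and the Wald p-value went to 1. The q2w contrast stayed finite (rate ratio 0.82). With the interaction removed, the same data gave a stable qw rate ratio of 0.50 (90% CI 0.18 to 1.40, p = 0.27).

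**When no cell is empty.** With equal rates and Poisson counts, stratum s contributes a log rate ratio with variance proportional to 1/n_s. If the two strata are weighted equally, the variance relative to the main-effects model is 0.25 × (1/0.34 + 1/0.66) = 0.25 × (2.94 + 1.52) = 1.11. The equal weighting is an assumption.

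**The case against.** The interaction is a coherent choice. Other exploratory models in the SAP carry stratum-by-treatment terms, and SAP Table 1 explains why background therapy matters. The endpoint is exploratory, by-stratum counts will be reported whatever the model does, and a failure would be plain from an enormous standard error. All of this stands, and it keeps the severity low.

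Four stronger readings are tempting, but the documents do not support them:

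- **Any empty cell of the six breaks the qw gate.** Only the four qw and placebo cells enter that comparison, so the six-cell probabilities must not be attached to it.
- **No usable result would remain.** In the illustration, a rate ratio standardized to the stratum mix stayed finite at 0.50, and a 2-df likelihood-ratio test gave p = 0.13. The SAP specifies neither, so they do not rescue the plan as written, but they show that the gap could also be closed by specification.
- **The plan weights the strata equally.** It states no weights. The 11% variance penalty applies only if equal weights are used.
- **Hospitalizations carry the same risk.** SAP 2.4.4.2.3.2 uses the same model, but no hospitalization rate is available. The empty-cell risk there is unquantified, and smaller if events are more frequent.

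The likelihood of failure is also conditional. It runs from likely at 0.03 per year to small at 0.15, and the documents do not say where in that range this trial falls.

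**Conclusion.** The concern holds as a conditional one. As written, the exacerbation analysis has no defined overall rate ratio, because stratum weights are not stated. If a relevant cell is empty, a stratum-averaged log rate ratio with its Wald CI and test cannot be estimated. For the qw comparison that gates q2w, the chance of this is about 68%, 36%, 13% and 6% at 0.03, 0.05, 0.08 and 0.10 events per patient-year. These figures rest on assumed equal Poisson rates, the 66/34 split at the cap and complete follow-up to Day 375. Overdispersion, dropout or an effective drug would raise them; a more even split or a higher event rate would lower them. The consequence is confined to an exploratory endpoint tested at 10% in its own hierarchy. Severity is low.

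**What to change.** In SAP 2.4.4.2.3.1 and Appendix B, fit the main negative binomial model with treatment and stratum only and log follow-up time as offset, in line with the 52-week Cox models. Take the rate ratios, 90% CIs and ordered tests from that model, and name the test type. Keep the planned counts by arm and background therapy status, and fit the interaction only as a separate exploratory test.

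The main-effects model loses a contrast only if a whole arm or a whole stratum has no events. The chance that at least one of the three arms is empty is 1 − [1 − exp(−100·r·T)]³. That is 1.8% at 0.05 (2.5% with k = 3) and 0.1–0.2% at 0.08. It is still 13–15% at 0.03, so a one-line fallback for an empty arm is worth adding.

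The cost is one model term. The by-stratum effect is then shown descriptively or in the separate model. A sponsor who prefers to keep the interaction would need to state the weights, the test and a sparse-cell fallback before unblinding. The wording in SAP 2.4.4.2.3.2 can be aligned for consistency.

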#### 2.4.4.2.3.2 Respiratory and non-elective hospitalizations endpoints

The numbers of respiratory and non-elective hospitalizations and the numbers of patients having at least one respiratory or at least one non-elective hospitalization will be described in the mITT population by treatment arm and background therapy status separately.

The annual rates for respiratory and non-elective hospitalizations in patient-year by treatment arm, the rate ratio and its 90% CI for each active arm versus placebo will be determined separately using a negative binomial model adjusted on the stratification factor variable and containing the stratification factor-by-treatment interaction. The SAR156597 qw arm will be tested versus Placebo at a type I error level of 10% first and if significant, will the SAR156597 q2w arm be tested versus Placebo at a two-sided type I error level of 10%.

The number (%) of patients with any hospitalization, the type of hospitalization (elective, non-elective) and the reason (respiratory, other reason) will be provided by treatment arm and background therapy status for hospitalization occurring between randomization and Day 375.

Furthermore, a listing with details of reasons (respiratory and other reason) will be displayed.

#### 2.4.4.2.3.3 Change from baseline in 6-MWT distance endpoint

The absolute change from baseline in 6-MWT distance endpoint will be analyzed on the mITT population. Assessments at week 52 will be used regardless of whether the patient has previously discontinued treatment. No imputation will be performed for the week 52 missing values of 6-MWT distance. Only patients having a baseline and a post-baseline 6-MWT distance values in at least one time points analysis window will be considered in the analysis.

The absolute change from baseline in 6-MWT distance at 52 weeks will be analysed using a Mixed Model with Repeated Measures (MMRM) with the fixed categorical effects of treatment arm, stratification factor (with/without Background Therapy), time point, treatment-by-time point interaction, stratification factor-by-treatment-by-time point interaction, supplemental oxygen use (Yes/No answer to the “Does the subject need oxygen therapy” question on the “Idiopathic Pulmonary Fibrosis History” e-CRF page) recorded at baseline, as well as the continuous fixed covariate of 6-MWT distance at baseline will be used. Parameters will be estimated with the Newton-Raphson algorithm, an unstructured covariance matrix will model the within-patient errors, and the denominator degrees of freedom will be estimated using Satterthwaite’s approximation.

The SAR156597 qw arm will be tested versus Placebo at a type I error level of 10% first and if significant, will the SAR156597 q2w arm be tested versus Placebo at a two-sided type I error level of 10% using the appropriate contrast. The adjusted Least Square Means (LSMeans) estimates and standard errors (SE) will be provided for each of the 3 arms, adjusted differences of means (LSMEAN differences), corresponding standard errors (SE) and 90% CIs will be assessed for each active arm versus placebo.

Descriptive statistics for values and changes from baseline in 6-MWT distance in the mITT population will be presented by treatment arm and background therapy status for each time point. The mean (SD) 6-MWT distance values and the mean (SD) absolute change from baseline in 6MWT distance over time will be graphically represented by treatment arm and by background therapy status.

The representation of LSmeans (SE) over time will be displayed by treatment arm and background therapy status.

In addition, to assess the quality of data:

- the number (%) of patients having a completed 6 minute walking test,
- the distribution of the time walked (in seconds) for those who did not complete 6-MWT,
- the number (%) of patients with any pause or break
- the distribution of the duration of pause (in seconds)

will be resumed by time point.

#### 2.4.4.2.3.4 Change from baseline in HRCT lung interstitial score endpoint

The absolute change from baseline in HRCT lung interstitial score endpoint will be analyzed on the mITT population. Assessments at week 52 will be used regardless of whether the patient has previously discontinued treatment. No imputation will be performed for the week 52 missing values of HRCT lung interstitial scores. Only patients having both the baseline and week 52 Total Fibrosing ILD score assessments available will be considered in the analysis.

The change from baseline at 52 weeks in Total Fibrosing ILD score will be analyzed using an ANCOVA model with fixed effect for treatment arm, adjusted on baseline Total Fibrosing ILD score, Emphysema total score at baseline, and the stratification factor (with/without Background Therapy) covariates, with a stratification factor-by-treatment interaction will be performed. The SAR156597 qw arm will be tested versus Placebo at a two-sided type I error level of 10% first and if significant, will the SAR156597 q2w arm be tested versus Placebo at a two-sided type I error level of 10% using the appropriate contrast. The adjusted Least Square Means (LSMeans) and their 90% CIs will be assessed for each treatment arm.

Descriptive statistics for values and changes from baseline in Total Fibrosing ILD score will be described over time by treatment arm and by background therapy status. The mean (SD) Total Fibrosing ILD score values and the mean (SD) absolute change from baseline in Total Fibrosing

ILD score over time will be graphically represented by treatment arm and by background therapy status.

The representation of LSmeans (SE) over time will be displayed by treatment arm and background therapy status for the Total Fibrosing ILD score.

In addition, descriptive statistics for values and changes from baseline in pattern score and the Emphysema total score will be described over time by treatment arm and by background therapy status. The mean (SD) scores values and the mean (SD) absolute change from baseline in scores over time will be graphically represented by treatment arm and by background therapy status.

